Appendix F. Tipping Point Analysis

Tipping Point Analysis for ACR20

To assess the robustness of the primary analysis using NRI-C data handling, tipping point analysis is conducted on ACR20 at Week 24. The analysis is conducted on the FAS using AO data, i.e., all observed data regardless of study drug adherence or rescue.

The tipping point analyses are two-dimensional, i.e., assumptions about the missing outcomes on the risankizumab treatment group and the placebo group can vary independently. Missing binary values are first imputed via MI under MAR assumption using the FCS method with the logistic regression option. Two sets of shift parameters are applied to the imputed values by adding two MNAR statements to the same PROC MI, which allows the missing ACR20 response rate to systematically vary from 0% to 100% in both risankizumab and placebo, respectively. This is accomplished by modifying the predicted probabilities for the responses through shifting the log odds (shift parameters are log odds ratios)⁵, then directly sampling the missing ACR20 response from the Bernoulli distribution with the modified probabilities. Sample codes are as follows:

```
proc mi data=data2 seed=&seed nimpute=30 out=mnar_imp;
class &predcate &postout;
fcs reg(BLj= &predcate &predcont, excluding BL);
fcs logistic(week4=&predcate &predcont);
fcs logistic(week8=&predcate &predcont week4);
fcs logistic(week12=&predcate &predcont week4 week8);
fcs logistic(week16=&predcate &predcont week4 week8 week12);
fcs logistic(week24=&predcate &predcont week4 week8 week12 week16);
by treatment;
var &predcate &predcont &postout;
mnar adjust(wk24(event="1") /shift=&sj1 adjustobs=(&treatment="PBO"));
mnar adjust(wk24(event="1") / shift=&sj2 adjustobs=(&treatment="RIS"));
run;
```

Note: &predcate (categorical covariates): gender, race (white vs. non-white), ethnicity, geographic regions, concomitant csDMARD at baseline (yes vs no), prior biologic use, extent of psoriasis, and intercurrent event status. &predcont (continuous covariates): age, baseline BMI, duration of PsA, 7 baseline ACR components. &postout: ACR20 binary values at week 4, week 8, week 12, week 16, week 24. BL_j is the jth

baseline ACR components in the order of TJC, SJC, Pain, PGA, PhGA, HAQ-DI, CRP.

For each pair of shift parameters, the same CMH method used for the primary analysis will be performed on each of the multiple imputed datasets to obtain the results for each comparison of the risankizumab treatment group versus the placebo group adjusted by stratification factors. PROC MIANALYZE will then be used to aggregate the results for the final statistical inference using Rubin's method.

If one pair of shift parameters are found to just reverse the study conclusion, in terms of p-value larger than 0.05, then the shift parameters are identified as the tipping point. The results for a grid of shift parameter combinations are provided in tabular format.

Tipping Point Analysis for HAQ-DI

To assess the impact of potential departures from the MAR assumption, tipping point analyses are conducted as a sensitivity check for change from baseline in HAQ-DI at Week 24.

The tipping point analyses are two-dimensional, i.e., assumptions about the missing outcomes on the risankizumab treatment group and the placebo group can vary independently. Missing values are first imputed via MI under MAR assumption using AO data, and then a shift parameter is applied to the imputed values (a different shift parameter may be specified for each treatment group). This is implemented by PROC MI using the MNAR statement. The imputation model uses FCS method, thus does not rely on a monotone missing pattern. It includes the same variables as for binary endpoint and is also stratified by treatment group. The number of imputed datasets is 30 for each PROC MI.

In cases where the shifted values are smaller than the minimum or larger than maximum value of the endpoint, (i.e., out of range), the minimum or maximum value of the endpoint is used in further analysis steps. For each pair of shift parameters, the SAS procedure PROC MIXED is used for ANCOVA model which includes the fixed effects of treatment,

stratification factors and the continuous fixed covariate of baseline measurement on each of the imputed datasets to obtain the results for each risankizumab treatment group versus the placebo group comparison. These results will be aggregated using Rubin's method to get p-values.

If a pair of shift parameters are found to just reverse the study conclusion, in terms of p-value larger than 0.05, then the shift parameters are identified as the tipping point. The results for a grid of shift parameter combinations are provided in tabular format.

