2.2 Study Design

This is a Phase 3, global, multi-center study that will evaluate moderately to severely active PsA patients. The subject population will consist of no more than 50% with an inadequate response (lack of efficacy after a minimum 12 weeks duration of therapy) or intolerance to 1 or 2 biologic therapies (Bio-IR). The remaining study population will be subjects who have an inadequate response (lack of efficacy after a minimum 12 weeks duration of therapy) or intolerance to at least 1 conventional synthetic disease modifying anti-rheumatic drugs (csDMARDs).

The study consists of a Screening Period (approximately 35 days), Period 1, Period 2 and a 20-week Follow-up Period. Period 1 is a 24-week randomized, double-blind, placebo-controlled, parallel-group period. Period 2 starts at Week 24. To maintain the blind to the original treatment allocation, treatment at Week 24 will be blinded: subjects randomized to placebo will receive blinded risankizumab 150 mg, and subjects randomized to risankizumab will receive blinded placebo. At Week 28 and for the remaining dosing visits (up to Week 208), all subjects will receive open-label risankizumab 150 mg every 12 weeks. Subjects will remain blinded to the original randomization allocation for the duration of study.

A schematic of the study is shown in [Figure 1](#).

Figure 1. Study Schematic

LEGEND:

BL = Baseline; RCT = randomized clinical trial; W = Week

* At Week 24, subjects randomized to placebo in Period 1 will receive a blinded dose of risankizumab. Subjects randomized to risankizumab treatment in Period 1 will receive a blinded dose of placebo.

** At Week 28, subjects randomized to placebo in Period 1 will receive a 2nd dose of risankizumab. Subjects randomized to risankizumab in Period 1 will receive risankizumab (scheduled dose).

*** From Week 40 and up to Week 208 Visits, doses occur q12w.

† Follow up phone call.

↑ Dosing.

◆ Bilateral radiographs of hands and feet if required for CASPAR criteria.

a. At Week 16, subjects classified as non-responders (defined as not achieving at least a 20% improvement in either or both tender joint count [TJC] and swollen joint count [SJC] at both Week 12 and Week 16) compared to Baseline will add or modify rescue concomitant medications/therapy as described in Section 5.4 of the study protocol. Rescue therapy qualification occurs only at Week 16 Visit.

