- b. Subject who does not have evaluation during a specific visit window due to reasons other than COVID-19 infection or logistical restriction related to COVID-19 pandemic will be handled by NRI for that visit. NRI will consider a subject with missing evaluation as a non-responder with the exception for composite binary endpoints including ACR20, ACR50, ACR70, MDA and modified PsARC for which the missing components will be imputed with last observation carry forward to derive composite score before imputing missing evaluations as a non-responder.
- c. Subjects will be considered as non-responders after initiation of rescue medication or initiation of concomitant medications for PsA that could

meaningfully impact efficacy assessment; these medications will be identified prior to database lock and unblinding.

For composite binary endpoints including ACR20, ACR50, ACR70, MDA and modified PsARC, the missing binary values due to COVID-19 infection or logistical restriction will be imputed via MI with the logistic regression option as outlined in [Appendix F](#). For other binary endpoints which are dichotomized from a continuous scale, the MI will be applied to the original continuous scale and the dichotomized endpoint will be derived from the imputed value for missing due to COVID-19 infection or logistical restriction.

Mixed-Effect Model Repeated Measures (MMRM)

The repeated measures analysis will be conducted using a mixed model including observed measurements at all visits. For the MMRM analysis, data collected after initiation of rescue medication or initiation of concomitant medications for PsA use that could meaningfully impact efficacy assessment will be excluded. The mixed model includes the categorical fixed effects of treatment, visit and treatment-by-visit interaction, stratification factors, and the continuous fixed covariate of baseline measurement. An unstructured variance covariance matrix will be used. Parameter estimation is based on the assumption of data being missing at random and using the method of restricted maximum likelihood (REML). The MMRM approach is appropriate in handling missing data due to COVID-19 infection or logistical restriction given the validity of the missing at random assumption. MMRM will be used for the primary estimand of continuous variables (refer to Section 8.4.1).

As Observed (AO)

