The AO analysis will not impute values for missing evaluations, and thus a subject who does not have an evaluation on a scheduled visit will be excluded from the AO analysis for that visit. Regardless of premature discontinuation of study drug, initiation of concomitant medications for PsA use that could meaningfully impact efficacy assessment,

or initiation of rescue medication, all observed data will be used in the analysis. The AO analysis will be used to facilitate the supplementary analysis.

AO with Imputation

The AO with imputation will use all observed data regardless of premature discontinuation of study drug, initiation of concomitant medications for PsA use that could meaningfully impact efficacy assessment, or initiation of rescue medication and will impute missing as non-responders. It will be used for the supplementary analysis for binary variables.

Multiple Imputation (MI)

As a sensitivity analysis, MI will be utilized for both hypothetical and treatment policy estimand ([Appendix D](#)). MI analysis will be performed based on AO data. The MI analysis will impute missing data multiple times under appropriate random variation and thus generate multiple imputed "pseudo-complete" datasets. SAS PROC MI will be used to generate 30 datasets using the fully conditional specification (FCS) method. Specifically, treatment group is included in the FCS imputation model to enable stratified sampling. Additionally, the imputation model includes demographics variables, baseline disease characteristics, stratification factors, as well as longitudinal response observed at any other visits. Analysis using CMH for binary endpoints and analysis of covariance (ANCOVA) for continuous endpoints will be performed on each of the multiple imputed datasets. Subsequently SAS PROC MIANALYZE will then be used to aggregate the results for the final statistical inference using Rubin's method.¹

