8.4 Secondary Efficacy Analyses

8.4.1 Secondary Efficacy Analyses

The secondary endpoints are defined in Section 3.2. Ranked secondary endpoint will be tested in rank order, according to procedures in Section 12.0.

For all binary secondary endpoints, frequencies and percentages will be reported for each treatment group. The primary estimand and analysis method are the same as that for the primary efficacy endpoint as defined in Section 8.3.4. NRI-C missing data handling will be used to analyze the primary estimand (refer to [Appendix D](#)).

For the secondary endpoints applicable only for a sub-population, the estimand will be constructed similarly but based on the sub-population, as defined in the below table.

Endpoint	Sub-population
Psoriasis Area Severity Index (PASI) 90 response at Week 24	Subjects with BSA $\geq 3\%$ at baseline are included in the analysis
Resolution of enthesitis (LEI = 0) at Week 24	Subjects with baseline presence of enthesitis (LEI > 0) are included in the analysis
Resolution of dactylitis (LDI = 0) at Week 24	Subjects with baseline presence of dactylitis (LDI > 0) are included in the analysis

For continuous secondary efficacy variables, primary analysis will be based on the hypothetical estimand. The attributes of the corresponding estimand are outline in [Appendix D](#). The comparison is risankizumab 150 mg vs placebo for patients randomized and treated with at least one dose of study drug. Statistical inference will be conducted using the MMRM model and the associated data handling as described in Section 8.2. The least square (LS) mean and 95% CI for each randomized treatment group and the LS mean treatment difference, the associated 95% CI and the p-value between risankizumab 150 mg group and the placebo group will be provided.

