8.4.2 Supportive Secondary Efficacy Analyses

For all binary secondary endpoints, the same CMH analyses as the supplementary analyses will be conducted using AO data and AO with imputation. The corresponding supplementary estimand is the same as defined in Section 8.3.4 except for the definition of the efficacy measurement (refer to [Appendix D](#)).

For continuous secondary endpoints, supplementary analyses on the FAS will be performed based on AO data using the treatment policy estimand framework (refer to [Appendix D](#)). The statistical inference will be conducted using ANCOVA model including treatment as the fixed factor and the corresponding baseline value and the stratification factor as the covariates. The LS mean and 95% CI will be reported for each randomized treatment group; the LS mean treatment difference and associated 95% CI and p-value will be reported comparing risankizumab 150 mg with the placebo group.

For HAQ-DI at Week 24, additional supplementary analysis will be conducted using MI as outlined in Section 8.2 based on AO data under MAR assumption. To assess deviations from MAR, the tipping point analysis will also be conducted using MI as additional sensitivity analyses. Details of the MI and tipping point analysis are outlined in Appendix F.

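### The HAQ-DI multiple imputation and tipping point use as-observed data, so no planned analysis varies missing-at-random for the post-rescue values that the primary MMRM deletes

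*SAP*

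**What the plan says.** **Primary HAQ-DI analysis.** SAP 8.4.1 states: "For continuous secondary efficacy variables, primary analysis will be based on the hypothetical estimand". Appendix D defines that estimand as the outcome had subjects not been rescued or started impactful PsA medication. The MMRM in SAP 8.2 implements it by deletion: "data collected after initiation of rescue medication or initiation of concomitant medications for PsA use that could meaningfully impact efficacy assessment will be excluded". Estimation assumes missing-at-random.

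**Multiple imputation (MI).** SAP 8.2 says: "As a sensitivity analysis, MI will be utilized for both hypothetical and treatment policy estimand". It then says: "MI analysis will be performed based on AO data". As-observed (AO) data, defined in the same section, keep every measured value whatever rescue or medication was started.

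**HAQ-DI supplements.** SAP 8.4.2 plans an ANCOVA on AO data under the treatment-policy estimand. For HAQ-DI at Week 24, "additional supplementary analysis will be conducted using MI as outlined in Section 8.2 based on AO data under MAR assumption", and "the tipping point analysis will also be conducted using MI as additional sensitivity analyses". Appendix F gives the mechanics: "Missing values are first imputed via MI under MAR assumption using AO data, and then a shift parameter is applied to the imputed values".

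**Rescue timing.** The note to the schematic in SAP 2.2 says: "Rescue therapy qualification occurs only at Week 16 Visit".

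**ACR20.** SAP 8.3.4 attaches the ACR20 tipping point to the supplementary MI on AO data. Appendix F says its purpose is to test the robustness of the NRI-C primary analysis, but also runs it on AO data.

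**The concern.** A sensitivity analysis should vary the assumption on which the main result rests. For the HAQ-DI MMRM, that assumption includes missing-at-random for the values it removes after rescue or impactful medication. Joint-count non-response triggers rescue (Protocol 5.4), whereas the MMRM conditions on treatment, visit, stratification factors, baseline and the subject's HAQ-DI history. The assumption is therefore open to question for these values in particular.

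Of the Period 1 assessments, only Week 24 falls after the Week 16 rescue decision. For a rescued subject, the value the MMRM deletes is thus the endpoint value itself. In AO data it counts as observed and is left alone.

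At stake is interpretation. Appendix F names no estimand for the HAQ-DI tipping point and defines tipping as reversal of the study conclusion. SAP 8.2 implies that MI covers the hypothetical estimand. A reader could take a reassuring AO tipping point as support for the MMRM result tested in the hierarchy.

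**Working it through.** **1. Which values each analysis touches (HAQ-DI, Week 24)**

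| Value | MMRM (hypothetical) | MI and tipping point on AO data |
|---|---|---|
| Observed, no rescue or impactful medication | used | used |
| Missing (dropout, COVID-19) | missing-at-random | imputed and shifted |
| Observed after rescue or impactful medication | deleted, missing-at-random | used as measured, never shifted |
| Missing after rescue or impactful medication | missing-at-random | imputed and shifted |

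The third row is the gap. The AO ANCOVA also uses those values as measured, so it does not fill it. Intercurrent event status is in the imputation model, but it only informs values that are missing in the AO data.

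**2. The plan's own figure (SAP 2.4)**

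Inputs: 210 per arm, 10% dropout, difference 0.24, SD 0.72, two-sided 0.05.

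- Evaluable per arm = 210 × 0.90 = 189
- SE = 0.72 × √(2/189) = 0.0741
- Power = 90.0% (normal) or 89.8% (t), which reproduces the stated figure of about 90%

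**3. Tipping shift on AO data**

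A positive shift means worse HAQ-DI. It is applied to the risankizumab arm only, with the placebo shift held at 0.

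- Critical difference = t(376) × SE = 1.966 × 0.0741 = 0.1456
- Slack = 0.24 − 0.1456 = 0.0944
- Tipping shift = 0.0944 / 0.10 = **0.94**

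**4. Tipping shift with post-event values also imputed and shifted**

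Rescue rates are assumed. For rescue rate r, the imputed share of an arm is m = 0.10 + 0.90 × r, and the tipping shift is slack / m for the risankizumab arm. The first version keeps SE at 0.0741. The second takes SE from the 210 × (1 − m) observed subjects left in each arm.

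| Rescue, risankizumab / placebo | m, risankizumab | Shift, SE kept | SE recomputed | Slack | Shift, SE recomputed |
|---|---|---|---|---|---|
| 5% / 15% | 0.145 | 0.65 | 0.0782 | 0.0862 | 0.59 |
| 10% / 20% | 0.190 | 0.50 | 0.0805 | 0.0817 | 0.43 |
| 15% / 15% | 0.235 | 0.40 | 0.0803 | 0.0819 | 0.35 |

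At 5%/15%, about 9 risankizumab values (210 × 0.9 × 0.05) and 28 placebo values (210 × 0.9 × 0.15) escape the AO grid. The 21 dropouts per arm are shifted.

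**5. When the gap closes**

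Step 4 uses the same 0.24 for both versions. If post-rescue data reduce the AO difference, the AO tipping shift falls too. The two shifts are equal when the AO difference = 0.1456 + 0.10 × (shift in step 4). This gives 0.211–0.205 at 5%/15%, 0.195–0.189 at 10%/20% and 0.186–0.181 at 15%/15%, so about 0.18 to 0.21 overall.

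**6. Both arms shifted**

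With an equal shift k in both arms at 5%/15%, the risankizumab disadvantage changes by (0.145 − 0.235) × k = −0.09k. That is movement in favour of risankizumab, so the full two-dimensional grid can go either way.

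Truncation to the HAQ-DI range and the variance added by the shift itself are ignored throughout.

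**The case against.** The best defence is that SAP 8.4.2 is coherent when read alone: it presents the HAQ-DI MI and tipping point as supplements on AO data. The AO ANCOVA and MI also show the result with the measured post-event values in place, which is useful evidence on whether the conclusion depends on deleting them. Both points stand. They do not remove the conflict inside SAP 8.2, and the AO analyses target a different estimand without varying missing-at-random for the deleted values.

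A second defence is that no section promises a departure-from-missing-at-random analysis for the hypothetical estimand, since MI is itself a missing-at-random method. That is correct. Wording alone could cure the contradiction, and the extra run is a design recommendation. Without it, however, the tested MMRM result has no such check.

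A third is that the illustrated drop in the tipping shift is largely mechanical, because spreading a shift over more values needs less per value. This also stands, and steps 5 and 6 of the working limit the claim accordingly.

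A reader might infer more than the documents support:

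- **That the ACR20 conflict is harmless because the conclusion would survive the worst corner of the grid.** This depends on the reading of the planning rates. If 55% and 35% already count dropouts as non-responders, the corner is 55% against 45%, z = 0.10/√(0.25 × 2/210) = 2.05, p = 0.04. If 10% dropout is taken off, it is 0.9 × 55% = 49.5% against 0.9 × 35% + 10% = 41.5%, p = 0.10 (both unstratified). Neither outcome should be claimed.
- **That Week 12 and 16 joint counts must enter the imputation model because they decide rescue.** The MMRM does not contain them, so adding them would move the zero-shift cell away from the analysis being tested. Protocol 5.4 also says qualifying subjects will receive rescue, so the model would largely extrapolate.

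**Conclusion.** The point holds for HAQ-DI. SAP 8.2 assigns MI to the hypothetical estimand on data that cannot serve it, and no planned analysis varies missing-at-random for the observed post-event values that the MMRM deletes. This follows from the text and needs no assumed rate.

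The size is illustrative. The one-arm tipping shift falls from about 0.94 to between 0.65 and 0.35 HAQ-DI units. This rests on assumed rescue rates, the SAP's 10% dropout, a placebo shift of 0 and the same 0.24 difference under both estimands. A less favourable result over the whole grid is possible but not established.

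The ACR20 part is a labelling conflict between Appendix F and SAP 8.3.4; relabelling does not change the computed grid.

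A reader might infer that the confirmatory result itself is compromised. The documents do not support that: the primary tests, type I error control and sample size do not depend on these sensitivity analyses.

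**What to change.** 1. Add one HAQ-DI MI and tipping-point run in which values after rescue or impactful PsA medication are set to missing, as in the MMRM. Impute them under missing-at-random and shift them on the planned two-dimensional grid. Leave intercurrent event status out of the imputation model in this run: no subject with an event keeps a Week 24 value, so its Week 24 effect cannot be estimated. Adding Week 12 and 16 joint counts is optional and should be reported as a further variant, because it changes the missing-at-random assumption relative to the MMRM.
2. Correct the MI paragraph in SAP 8.2 and the purpose sentence for ACR20 in Appendix F, and name the estimand of each tipping-point run in Appendix F. Keep the AO versions as treatment-policy supplements.

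The cost is SAP wording and one extra run of planned code on a second input dataset. The sponsor should accept that the HAQ-DI result may look less robust.
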